## 2.2 RATIONALE

**The objective of this experiment is to experimentally determine the pathophysiological role of perimenstrual ovarian steroid hormone withdrawal on acute suicide risk.** Suicidal behavior arises from two proximal risk factors: **Suicidal desire**, defined as the wish to die, and **suicidal action capacity**, defined as a readiness to act on suicidal urges. **Hopelessness** and **Negative social appraisals** are constructs reflecting dysregulation in central reward and social processing networks, and, in turn, strongly predict **suicidal desire**. **Poor inhibitory control** and **threat sensitivity** (cognitive bias to interpret stimuli in a threat-related manner) are constructs reflecting dysregulation in central cognitive control and threat avoidance networks, and, in turn, are strong predictors of **suicidal action capacity** (right side of Figure at right).

[figure not shown]

Figure 1. Pathophysiologic Model of Increased Perimenstrual Suicide Risk

The **RATIONALE** for examining ovarian steroid withdrawal in suicide risk stems from evidence that withdrawal from estradiol (E2) and progesterone (P4), such as that occurring naturally during the perimenstrual timeframe, modulate each of the mediating constructs and associated clinical symptoms (Figure above) toward risk, exerting robust anxiogenic, depressogenic, and impulsogenic effects in animals and increasing depression, anxiety, rejection sensitivity, and impulsivity in susceptible women (preliminary work by PI). **However, no experimental work has directly evaluated whether perimenstrual E2/P4 withdrawal influences suicidality.** The experiment will determine the effects of perimenstrual E2/P4 withdrawal on suicidal desire and action capacity in at-risk women, testing mediation by risk-related behavioral constructs.

**Design Overview:** 30 female outpatients with suicidal ideation but minimal imminent risk for attempt will complete behavioral tasks measuring *hopelessness, social appraisals, inhibitory control, and threat sensitivity* as well as clinical interviews in each of two conditions (order randomized across two menstrual cycle phases): (1) natural **perimenstrual E2/P4 withdrawal (placebo)**, and (2) **exogenous stabilization of physiologic premenstrual (luteal phase) E2/P4 to prevent withdrawal**. Daily calls will also assess symptoms and suicidality.

**CENTRAL HYPOTHESIS: Experimentally test a pathophysiologic mediational model** in which late luteal (perimenstrual) E2/P4 withdrawal (vs. experimental luteal E2/P4 stabilization) increases suicidal desire (via increased hopelessness and negative social appraisals) and suicidal action capacity (via reduced inhibitory control and increased threat sensitivity). We predict that natural E2/P4 withdrawal (compared to stabilization) will increase reports of suicidal desire (partially mediated by task performance indicating increased hopelessness and negative social appraisals) and action capacity (partially mediated by task performance indicating decreased inhibitory control and increased threat sensitivity).

### **JUSTIFICATION OF E2/P4 DOSING AND SCHEDULE**

In collaboration with Drs. [name], [name], and [name], the PI has chosen formulations that are bioidentical to human E2 and P4 and will mimic luteal phase concentrations or E2 and P4.

**General Rationale for Route and Dose of E2 and P4.** We will use Climara® 7 day transdermal E2 patches. Peak levels of E2 with Climara (~45 pg/mL), achieved within 24 hrs., correspond roughly to normative luteal E2 levels. No transdermal P4 is available. Although transdermal synthetic progestins are available, these molecules have a high affinity for androgen and mineralocorticoid receptors, limiting their usefulness for testing our hypotheses. Thus, oral prometrium will be dosed b.i.d. to achieve luteal P4 levels to create more **steady-state levels** and minimize the variability that can occur with the oral route.

**Rationale for Timing and Duration of E2/P4.** Administration for 14 days, starting 7 days after a positive urine test for ovulation, will span the range of time in which natural perimenstrual withdrawal would occur and prevent natural withdrawal, thereby allowing us to determine the effects of natural hormone withdrawal vs. experimentally stabilized hormones across the same perimenstrual time period of the menstrual cycle.

**Compliance checks:** Participants will: **1)** be educated on the importance of replacing their patches every 7 days, with individualized strategies to enhance compliance; **2)** be asked about patch adherence and pill compliance on each daily call; **3)** record date of patch application on calendars, reviewed at lab visits; **4)** bring used and unused patches to visits; **5)** be given extra patches for immediate replacement; and **6)** **Serum Levels of E2 and P4** will be collected at each session to both confirm compliance and that exogenous hormones replicate physiologic luteal phase levels.

**Specific Rational for Route and Dose of Estradiol (E2).** By avoiding the first-pass metabolic effects of oral estrogen, **transdermal E2** creates more stable blood levels and a more physiologic profile of E2 relative to its metabolites estrone and estriol. Transdermal E2 also has a superior safety profile than oral estrogen for thromboembolic and metabolic risk. The use of a 7 day transdermal system provides significantly more

stable concentrations and fewer patch adherence problems than twice weekly patches. Climara® 7 day patches will be employed because the adhesive layer of the matrix patch (vs. reservoir systems) consists of polymeric acrylate or vinyl acetate in which the E2 molecules are distributed to continuously releases E2, which is transported across the skin leading to sustained circulating levels of E2 during each 7-day period. Levels of E2 achieved in pharmacological studies with Climara patches at the .1mg/24hrs dosage correspond roughly to normative luteal levels of E2. Climara achieves peak levels of E2 within 24 hours.

**Specific Rationale for Route and Dose of Progesterone (P4).** No transdermal P4 is available. Although transdermal synthetic progestins are available, these molecules have a high affinity not only for the progesterone receptor but also for the androgen and mineralocorticoid receptors, limiting their usefulness for testing our hypotheses. Therefore, 200mg oral prometrium will be dosed daily (100mg each morning, 100mg each evening) to achieve luteal levels P4 to create more steady-state levels and minimize the greater variability (peaks and troughs) that can occur with the oral route. Prometrium peaks within 3 hours and declines throughout the next 24 hours.

**Other possible hormone manipulations** were considered: a) mid-luteal administration of human chorionic gonadotropin to extend the luteal phase by preserving the corpus luteum, which would not isolate E2/P4 withdrawal from other hormones; b) mid-luteal GNRH antagonist administration to precipitously drop hormones, which would have a menopausal side effect profile and a precipitous decline in E2/P4 that would not resemble perimenstrual E2/P4 decline; c) use of continuous oral contraceptives to eliminate cyclical hormone flux, which would stabilize E2/P4 in follicular phase ranges and not allow modeling of luteal phase levels.

## 2.3 POTENTIAL RISKS AND BENEFITS

### 2.3.1 KNOWN POTENTIAL RISKS

#### 1) *Psychological Symptom Assessment*

Clinical interviews and self-report assessments contain questions regarding sensitive personal information, including severe psychological symptoms such as suicidal and other impulsive behaviors (e.g., substance abuse). As a result, participants may become upset or embarrassed when discussing current or past distressing life events and behaviors. On the other hand, recent evidence suggests that research questions pertaining to potentially distressing topics such as psychiatric symptoms, suicidality, and sexual or physical abuse do not significantly increase distress or acute suicide risk in women who report these issues. The chance of increased distress is necessary in order to assess how symptoms change in response to perimenstrual hormone withdrawal (vs. stabilization).

#### 2) *Effects of the Ovarian Hormone Stabilization Protocol on Mood/Anxiety and Behavior*

**Mood/Anxiety.** As the population being studied in this protocol will have elevated psychiatric symptoms, and as ovarian hormone changes are implicated in depressive symptoms in some women, it is possible that adverse mood reactions may occur (1) during the administration of ovarian hormones in the stabilization condition or (2) naturally during the placebo (natural) perimenstrual withdrawal condition. However, because the hormone manipulation mimics (i.e., stabilizes) the luteal hormone levels that women naturally experience, the study is not expected to pose any greater risk to participants than what they experience in daily life. Furthermore, although withdrawal from exogenous E2/P4 (which will mimic normal late luteal phase hormone withdrawal given that exogenous levels will mirror normal luteal physiologic ranges) could elicit negative mood changes, these would not be expected to be any more severe than those that would otherwise have arisen from normal perimenstrual hormone withdrawal—that is, we will have simply delayed the normal withdrawal process.

**Suicidality.** As detailed above, the population will be recruited to achieve a population of women that is simultaneously: (1) experiencing recent suicidal ideation, yet (2) at acceptably low current risk for

**suicidal crisis/attempt** based on an assessment conducted during a screening visit (see **Experimental Eligibility Table in later section**). Because ovarian hormone changes are implicated in psychiatric symptoms in some women, and because such symptoms may increase suicide risk, it is possible that increases in suicidality may occur (1) during the administration of ovarian hormones in stabilization conditions or (2) naturally during the placebo (natural) perimenstrual withdrawal condition. **However, because the hormone manipulation mimics (i.e., stabilizes) the normal physiologic range of luteal hormone levels that women naturally experience, the study is not expected to expose participants to greater risk for suicidality than what they experience in daily life.**

### **3) Hormone Side Effects**

We do not expect any adverse side effects associated with the hormonal manipulation for the following reasons: First, we will be administering the physiologically relevant steroid hormones (estradiol and/or progesterone) and not the substituted steroids (such as ethinyl estradiol or norethindrone) present in many oral contraceptives and which have been reported to have a potentially more serious profile of side effects. Second, prior exogenous hormonal studies (or E2, P4, or a combination) conducted in [name] lab at the NIH that induced substantially more elevated hormone concentrations and a more precipitous hormone withdrawal in women with mood disorders, and no severe psychological adverse events were reported.

#### **SIDE EFFECTS OF ESTRADIOL**

##### **The most frequent side effects associated with estradiol use include:**

- breast tenderness (occurs in 29% of patients)
- abdominal cramps (occurs in 16% of patients)
- headache (occurs in 13% of patients)
- edema (swelling) (occurs in 10% of patients)
- nausea (occurs in 6% of patients)
- acne (occurs in 3 – 12% of patients)
- skin rash or irritation may also occur at site where the patch is placed (occurs in 3 - 12% of patients)

##### **Rare side effects (<1%) include:**

- jaundice (yellowing of skin)
- increased blood pressure
- worsening of migraines or asthma
- enlargement of uterine fibroids
- intolerance to contact lenses
- dizziness
- changes in appetite and weight

E2 is widely prescribed; given the modest dose and duration administered here, severe adverse events are unlikely. Given our plans to administer transdermal E2 to women: (1) for only 14 days, (2) no older than 45 years of age, (3) who are currently regularly menstruating and medically healthy, and (4) who are at no greater than average risk for cancer and venous thromboembolism, the **risk of serious adverse events is exceedingly low.**

#### **SIDE EFFECTS OF PROGESTERONE**

##### **The most common side effects associated with progesterone include:**

- breast tenderness (occurs in 16% of patients)
- dizziness (occurs in 24% of patients)
- abdominal cramping (occurs in 20% of patients)

- headache (occurs in 16% of patients)
- viral infection (occurs in 12% of patients)
- joint pain (occurs in 12% of patients)
- diarrhea (occurs in 8% of patients)
- menstrual bleeding, sometimes consistent with a heavy menstrual period (occurs in 20-30% of patients)
- drowsiness (occurs in 9% of patients)

**Rare (<1%) side effects include:**

- vaginal discharge
- chest pain
- abdominal bloating

Progesterone is widely prescribed, with indications including dysfunctional uterine bleeding, endometriosis, mastodynia, galactorrhea, and precocious puberty. In our recent study, a dose of 300 mg of oral micronized progesterone (higher than that given in the present study) was given to a sample of women with premenstrual mood disturbance and was well tolerated by this sample. Given the modest dose and duration used in the present trial, severe adverse events are unlikely.

**4) Confidentiality**

A breach of confidentiality could indicate to others a participants' history of psychiatric symptoms.

**5) Venipuncture**

Standard risks associated with venipuncture are present during the laboratory testing sessions.

**2.3.2 KNOWN POTENTIAL BENEFITS**

*This is a mechanistic study to determine the role of ovarian hormone changes in constructs that are relevant to suicidality. There is no direct benefit to the participants other than the benefit of knowing that they are contributing to research on the causes of suicidality.*

**3 OBJECTIVES AND PURPOSE**

The purpose of this mechanistic study is to experimentally test a pathophysiologic mediational model in which late luteal (perimenstrual) E2/P4 withdrawal (vs. experimental luteal E2/P4 stabilization via exogenous transdermal E2 and oral micronized P4) increases suicidal desire (via increased hopelessness and negative social appraisals) and suicidal action capacity (via reduced inhibitory control and increased threat sensitivity). We predict that natural E2/P4 withdrawal (compared to stabilization) will increase reports of suicidal desire (partially mediated by task performance indicating increased hopelessness and negative social appraisals) and action capacity (partially mediated by task performance indicating decreased inhibitory control and increased threat sensitivity).

**4 STUDY DESIGN AND ENDPOINTS**

**4.1 DESCRIPTION OF THE STUDY DESIGN**

[figure not shown]
This is a single-center study; there is no phase designation because it is a mechanistic experiment with agents (E2,P4) that is commonly used in clinical practice.

**Participants:** 30 female outpatients with recent suicidal ideation but **low imminent risk for suicide attempt** (see **Human Subjects** section for details) receiving treatment as usual from a mental health provider at UNC will be recruited. Women must: be 18 to 45 years of age, have normal menstrual cycles (25-35 days), not pregnant (verified with urine screens), breastfeeding, or trying to get pregnant, not taking hormones, no history of serious medical illness, normal weight (BMI 18-28 kg/m^2), and low risk for thrombotic events (factor V Leiden mutation based on family history). Use of psychotropic medications are expected in the majority of participants. *Most outpatients with suicidality take psychotropic medications; therefore, to increase feasibility and generalizability, medication use will be carefully measured daily and covaried in analyses if common enough.*

**Psychiatric Diagnoses.** Women will undergo initial SCID-I and SCID-II interviews. *History of manic episode, psychosis (except dissociation), or substance abuse disorder will be exclusionary due to increased risk of suicidal crises.* Additionally, a self-report history of treatment for postpartum depression or a current diagnosis of premenstrual dysphoric disorder will be exclusionary, since these reproductive mood disorders could be characterized by a different pathophysiological pattern of sensitivity to ovarian steroid flux. On the basis of work by [name], we expect that 50 - 75% of our sample will meet criteria for major or persistent depressive disorder, ≥ 50% will meet criteria for BPD, and ≥ 25% will meet criteria for an anxiety disorder.

**Study Design (see figure at right; top = naturally occurring cyclicity of E2/P4 under placebo, bottom = E2/P4 withdrawal prevention using exogenous E2/P4). THIS IS NOT A CLINICAL EFFICACY TRIAL.** However, a within-person crossover RCT design with transdermal 17 $\beta$ -E2 and oral micronized P4 (or placebo) will investigate the pathophysiologic role of perimenstrual steroid withdrawal in suicidal desire and action capacity. Consenting participants will be trained in the protocol, including urine ovulation testing (LH surge preceding ovulation 24-36 hours), the daily phone assessment, and the patch/pill schedule. Using a double-blind, **within-subject cross-over design**, participants will be randomized as to the order in which they receive (1) active 17 $\beta$ -E2 + P4 or (2) placebo patch/pills. The UNC Investigational Drug Services will manage the randomization and dispensing of medications. During the E2/P4 stabilization condition, for two weeks, participants will wear a weekly patch (Climara®) delivering 0.10 mg E2/24 hrs—a dose tolerated by > 94% of the 200+ women in [name] recent study (NIMHR01087619)—

and will take oral progesterone (Prometrium®) at a dose of 200 mg (100mg each morning, 100mg each evening). A higher dose (300mg/day) was well tolerated by 100% of premenopausal women in [name] prior research (NIMHR01051246). These doses will achieve (stabilize) luteal E2/P4 levels.

**Timing of Hormone Administration.** Based on home urine ovulation testing, participants will apply the first seven-day transdermal E2 patch (or placebo patch) and begin daily oral P4 (or oral placebo) seven days after urine-confirmed ovulation (cycle 1, +7) to coincide with a time in the natural cycle when E2/P4 are elevated. The goal of the active E2+P4 manipulation is to **extend and maintain the mid-luteal phase hormone profile** beyond the point in the cycle that would normally be associated with natural E2/P4 withdrawal. In the active E2/P4 condition, the luteal phase hormone profile will be maintained for 14 days by applying a new patch on day 8 (extended luteal phase spanning +7 to +21 in lower panel), preventing natural withdrawal and stabilizing E2/P4 in physiologic luteal range. The placebo condition uses the same patch/pill schedule.

**Assessment of Outcomes.** Participants will complete phone measures of symptoms and suicidality starting on the first day of patches/pills and ending 5 days following the last patch/pill (phone symbols in figure above). Three lab sessions will measure mediating constructs using behavioral tasks. In each condition, lab visits will occur on days +7, +14, and +22 following ovulation.

**Primary Windows of Comparison for Hypothesis Testing.** To test whether prevention of E2/P4 withdrawal is associated with mediating behavioral constructs and suicide risk, we will compare tasks and interviews in **LABPL2** with **LABEXP2**.

**Blinding of Participants and Staff.** All study staff performing assessments will remain blinded to condition. The natural within-woman variation in menstrual cycle length from one cycle to another will help maintain the participant blind. Few women have regular 28 day cycles, and between-cycle variation up to 8 days is normal. Demand characteristics regarding the impact of hormonal manipulation will be minimized by informing participants that women vary a great deal in their responses to hormones, and our current evidence does not allow us to predict for certain whether hormones have a positive, negative, or neutral effect on women's symptoms (of note, this is scientifically accurate). Finally, although some women may become unblinded later in the extended hormone phase, work by the mentoring team suggests that pharmacologic delay of menses does not influence the course of perimenstrual mood symptoms.

**Lab Construct Measures.** Each computerized task is scored using within-task comparisons, controlling for experience- or training-related changes in response time. **Hopelessness** will be measured via the Future Thinking Implicit Relational Assessment Procedure (FT-IRAP), in which participants respond with *true* or *false* to pairings between "I expect" and "I don't expect" with sets of negative (e.g., worry, sadness) and positive (e.g., enjoyment, happiness) events. Greater latency to optimistic/hopeful, and lower latency to pessimistic/hopeless pairings indicate implicit hopelessness. **Validity:** Performance predicts clinical hopelessness and depression. Negative **Social Appraisals** will be measured using the Social Acceptance-Rejection Implicit Association Test (SAR-IAT), in which participants respond to pairings of *self* words (e.g., I, me) and *other* words (e.g., them, you) with words indicating social acceptance (e.g., included) or social rejection (e.g., rejected). Response times to pairings indicate the strength of implicit self-with-acceptance or self-with-rejection associations. **Validity:** Performance predicts explicit social appraisals and heightened negative affect in social interactions per clinical interviews. **Inhibitory Control** will be measured using performance on the Stop-Signal Task (SST), an index of the ability to withhold a prepotent response. **Validity:** Performance predicts prefrontal cortex function and lower impulsive clinical outcomes. **Threat Sensitivity** will be measured as attentional bias for threat pictures on a Dot Probe Task (DPT). **Validity:** Attentional bias to threat on this task is linked to anxiety disorders and multimodal indices of threat sensitivity in daily life.

**Daily Telephone Symptom Measures (PRIMARY AND SECONDARY ENDPOINTS): Depressive Symptoms and Hopelessness** using the 10-item short form of the CES-D and the Beck Hopelessness Scale, **Anxiety Symptoms** (reflecting Threat Sensitivity) using the 6-item short form of the Patient-Reported Outcome Measurement Information System (PROMIS) Anxiety scale; **Impulsive Symptoms** using a five item version of the UPPS-P Lack of Premeditation (i.e., classic impulsivity) subscale; and **Rejection Sensitivity Symptoms** (reflecting social appraisals) using two items with high item-total correlations from the Social Evaluation subscale of the State Self-Esteem Scale. *Each of these inventories has been extensively validated for the measurement of the target construct.* **Suicidal desire and action capacity** will be measured daily using a shortened version of the SITBI.

**Participant Safety:** Emergent changes in suicidality will be managed using the structured University of Washington Risk Assessment and Management Protocol (UWRAP), a safety protocol recommended by NIMH for RCTs since it allows for the safe study of individuals with suicidality. If imminent risk for suicide emerges and cannot be satisfactorily managed by the UWRAP protocol (as determined by [name]), the protocol for discontinuation will be followed. **However, because the manipulation mimics luteal E2/P4 levels that**

women naturally experience, the hormonal manipulation is not expected to pose greater risk than a normal menstrual cycle—the risk will simply be shifted in the stabilization condition.

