### 7.1.2 STANDARD OF CARE STUDY PROCEDURES

Although the LRAP/UWRAP dictates the provision of basic supportive conversation and other simple interventions to reduce imminent risk in the context of increased suicidality, participants are expected to utilize their mental health provider for any **treatment** needs that arise during the course of the study. Therefore, participation will require that the participant consents to phone contact between the PI and their current mental health provider in two circumstances: (1) one standard phone contact occurring prior to engagement in the first condition in which the PI describes the experiment and explains the protocol for daily risk assessment and discontinuation of participation should it be necessary; and (2) as-needed phone contact in the event that the participant must be discontinued to alert the provider to the severe change in mood symptoms or suicidality.

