## 7.5 CONCOMITANT MEDICATIONS, TREATMENTS, AND PROCEDURES

All concomitant prescription medications taken during study participation will be recorded. For this protocol, a prescription medication is defined as a medication that can be prescribed only by a properly authorized/licensed clinician. Medications to be reported are concomitant prescription medications, over-the-counter medications and non-prescription medications.

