### 7.5.1 PRECAUTIONARY MEDICATIONS, TREATMENTS, AND PROCEDURES

There are no medications that are prohibited for concomitant use with the study agents, with the exception of any hormonal preparations (that are exclusionary).

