## 7.6 PROHIBITED MEDICATIONS, TREATMENTS, AND PROCEDURES

There are no prohibited medications or procedures except hormonal preparations, which are exclusionary.

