#### 10.4.2 ANALYSIS OF THE PRIMARY EFFICACY ENDPOINT(S)

Primary and secondary endpoints are operationalized above (i.e., mean within-person differences between placebo and experimental in final seven days of manipulation) for the daily SITB suicidal ideation and planning subscales (primary endpoints) as well as the daily UPPS-P impulsivity, PROMIS anxiety, CESD depression, BHI hopelessness, and SSES rejection sensitivity subscales (secondary endpoints).

**Analyses will proceed identically for all outcomes listed above.** First, we will calculate each subject's mean daily rating (via phone) on the outcome measure *in the final seven days of both the placebo condition* (placebo mean score) and the experimental condition (experimental mean score).

Second, we will utilize paired samples t-tests to examine the within-person condition effect. If proposed covariates (medicines, BMI, age) show sufficient variability, we will instead use a repeated measures ANCOVA to evaluate the condition effect. These analyses will be conducted on the intent-to-treat dataset.

If necessary due to violations of model assumptions, we will utilize similar nonparametric tests.

---

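### The plan allows the primary within-woman contrast to be adjusted for medication taken during the conditions, which can remove part of the condition effect

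*Combined protocol and SAP*

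**What the plan says.** Section 4.1 states: "Use of psychotropic medications are expected in the majority of participants". It then says that "medication use will be carefully measured daily and covaried in analyses if common enough".

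Section 7.5.1 states: "There are no medications that are prohibited for concomitant use with the study agents", apart from hormonal preparations, and section 7.6 repeats this: "There are no prohibited medications or procedures except hormonal preparations, which are exclusionary". The documents contain no stable-dose rule for psychotropics. Under section 7.1.2, "participants are expected to utilize their mental health provider for any" treatment needs that come up while they are on study. Section 7.5 adds: "All concomitant prescription medications taken during study participation will be recorded".

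For the primary analysis, section 10.4.2 begins with the unadjusted test: "we will utilize paired samples t-tests to examine the within-person condition effect". It continues: "If proposed covariates (medicines, BMI, age) show sufficient variability, we will instead use a repeated measures ANCOVA to evaluate the condition effect". The same procedure applies to both primary and all secondary endpoints. No unadjusted estimate is retained once the ANCOVA is chosen. Neither trigger has a threshold, and section 10.1 says that there will be no formal SAP in which one could be set.

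**The concern.** The endpoint in section 4.2.1 is a within-woman difference, placebo minus stabilization, over the last seven days of each condition. A medication term can shift that difference only through use that itself differs between the two conditions. Such use occurs after randomization. On the protocol's own hypothesis, withdrawal under placebo worsens mood and suicidality, so women may take more medication in that condition because of the condition.

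An analysis that holds such use equal estimates what the difference would be among women with equal medication change. That is not the randomized condition effect under usual care. Because the adjusted model replaces the paired test, the altered quantity would become the primary result, with no unadjusted figure planned beside it.

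**Working it through.** **The plan's own figure.** No figure in the plan addresses medication use. The nearest is the claim in section 10.5 of 80% power for d = .40 with 30 completers. If d is the mean difference divided by the SD of the within-woman differences, a two-sided paired t-test at .05 with n = 30 has 56% power. Power reaches 78% if d is on the raw-score SD and the within-woman correlation is .7, which the plan does not state. That mismatch is a separate matter. The 56% serves here only as a starting point.

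**Inputs.** From the documents: d = .40, 30 completers and two-sided alpha .05 (sections 10.4.1 and 10.5). Assumed: how strongly medication use follows symptoms, and whether the medication helps.

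**Step 1: which covariates can move the contrast.** Write dY for a woman's outcome difference (placebo minus stabilization) and dM for her difference in medication use. An additive covariate with one value per woman has dM = 0 and cancels from dY. Only a covariate that varies between conditions matters.

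**Step 2: use follows symptoms and has no benefit of its own.** Let dM = b·dY + e, let μ be the mean of dY, and let r be the correlation of dM with dY. The slope of dY on dM is r²/b, so the adjusted condition effect is μ − (r²/b)(b·μ) = μ(1 − r²). With μ = .40:

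| r (assumed) | 1 − r² | adjusted effect | loss | simulated rejection rate, n = 30 |
|---|---|---|---|---|
| .3 | .91 | .364 | 9% | 50% |
| .5 | .75 | .300 | 25% | 42% |
| .7 | .51 | .204 | 49% | 30% |

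The unadjusted rejection rate is about 56%. Rates are from 20,000 replicates per setting.

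**Step 3: the medication works.** Let the symptom difference before any medication benefit be dL = τ + error. Let dM = λ·dL + error and dY = dL − β·dM, with all error SDs equal to 1. The unadjusted mean is τ(1 − βλ) and the adjusted one is τ/(1 + λ²). With τ = .40:

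| λ | β | unadjusted | adjusted | ratio |
|---|---|---|---|---|
| .5 | 0 | .40 | .32 | .80 |
| 1.0 | 0 | .40 | .20 | .50 |
| .25 | .4 | .36 | .376 | 1.04 |
| .5 | .4 | .32 | .32 | 1.00 |
| 1.0 | .4 | .24 | .20 | .83 |

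The adjusted figure does not depend on β. In general it recovers neither the effect under usual care, τ(1 − βλ), nor the effect without any medication response, τ.

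**Step 4: excluding women whose medication changed.** In the model of step 2, the mean of dY among women with dM = 0 is again μ(1 − r²). Simulation restricted to near-zero dM gave .364, .298 and .206 for r = .3, .5 and .7. Exclusion therefore carries the same distortion as adjustment.

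**The case against.** The strongest reply is that the covariate may be harmless. Section 10.4.2 lists medicines beside BMI and age, where variability can only mean variability across women, and a repeated measures ANCOVA conventionally takes one value per subject. On that reading the contrast is unchanged. This stands as a possible reading, but section 4.1 ties the covariate to daily measurement, which a fixed value would not need. The text supports either reading.

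Symptom-driven use is also an assumption. No section mentions as-needed psychotropics. Eligibility allows provider contact as infrequent as once every three months, while each condition lasts 14 days, which limits provider-led changes within a condition. This stands against any firm size. It does not rule out such use, because the plan restricts nothing except hormones and sends women to their providers when needs arise.

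A reader might infer three stronger things that the documents do not support:

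- That medication will be entered. Entry is conditional, though expected majority use makes the section 4.1 condition likely to be met.
- That the bias is largest when the trigger fires. Common use is not differing use: if every woman took a stable daily drug, use would be universal and the bias zero.
- That the primary estimate is pulled toward zero. Step 3 shows that an effective medication dilutes the unadjusted contrast too, so the adjusted estimate can be equal or slightly larger.

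**Conclusion.** The concern holds as a gap in the plan. As written, the plan permits the primary condition contrast to be replaced by one adjusted for medication taken during the conditions, and it does not define the covariate. If that covariate varies between conditions and responds to symptoms, the result no longer estimates the difference in section 4.2.1.

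The possible loss is 9% to 49% of d = .40, under assumed correlations of .3 to .7 and no benefit from the medication. None of these inputs is in the documents, and the upper end rests on the strongest correlation assumed. With an effective medication the direction relative to the unadjusted estimate is uncertain. With a value fixed within each woman there is no effect. The remedy is right under either reading of the covariate, so it does not depend on settling the size.

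**What to change.** In section 10.4.2, make the within-woman condition contrast, unadjusted for on-study medication, the primary analysis. Limit any medication covariate there to use recorded before randomization. Amend the sentence in section 4.1 on covarying daily medication use to match.

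Tabulate on-study psychotropic use, and any start, stop or dose change, by condition as an outcome. Any analysis that adjusts for on-study medication, or that leaves out women whose medication changed, should be supportive only and labelled as conditioning on a post-randomization variable.

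The cost is wording changes in two sections and one table from data already to be recorded. Any precision that might come from adjusting for medication changes unrelated to condition is given up. No change to permitted treatment is involved.
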